## **8.2. Treatment Assignment**

Screening materials from eligible subjects who are identified by the investigators as having met the inclusion and exclusion criteria (see below Table 9.2-1 and Table 9.3-1, respectively) and who provide written informed consent, will be reviewed by a Case Review Committee (CRC; see Section 22.2) to assess and confirm suitability of subjects for enrollment.

For the randomized cohort, eligible subjects will be randomized in a 2:1 allocation to receive either the Lotus Valve System (test) or a commercially available self-expanding CoreValve® Transcatheter Aortic Valve Replacement System (control). The randomization schedules will be computer-generated, using a pseudo-random number generator. Randomization will be stratified by center and by high or extreme risk status (see Section 26.2 for definitions). All randomized subjects will have unique identification numbers. Random permuted blocks will be employed to ensure approximate balance of treatment allocation within each stratum. Instructions on randomization are provided in the Manual of Operations. Subject should be randomized within 7 calendar days of CRC approval. Subjects should be treated within 14 calendar days of randomization and no later than 30 calendar days after randomization.

**Note:** There will be a non-randomized roll-in phase with only the test device for centers that do not have previous experience implanting the Lotus Valve; each of these centers will perform at least 2 roll-in cases before commencing randomization. All roll-in subjects will have unique identification numbers. Subjects receiving the 21 mm Lotus Valve will be enrolled in a non-randomized, nested registry cohort to assess safety and effectiveness. After enrollment of the randomized cohort is completed, subjects will be enrolled in a U.S. Continued Access Study cohort with the Lotus Valve (23 mm, 25 mm, and 27 mm valve sizes) to further assess performance and safety. Additionally, subjects will be enrolled in a non-randomized, nested registry cohort with the 23 mm, 25 mm or 27 mm LOTUS Edge Valve (LOTUS Edge Nested Registry) to confirm performance of the Lotus Valve implantation procedure with the Edge delivery system. There will also be a non-randomized, roll-in phase with the 29 mm LOTUS Edge Valve for centers that do not have previous

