#### 12.1.2.2. Sample Size Parameters for the Primary Effectiveness Endpoint

##### 12.1.2.2.1 Primary Hypothesis

The sample size calculation for the primary hypothesis of the primary effectiveness endpoint at 1 year is based on the following assumptions.

- Expected Lotus Valve (test) rate = 32%
- Expected CoreValve (control) rate = 32%

- Non-inferiority margin ( $\Delta$ ) = 9.5%
- Test significance level ( $\alpha$ ) = 0.025 (1-sided)
- Test : Control ratio = 2:1
- Power ( $1-\beta$ ) = 80%
- Total number of evaluable subjects = 819
- Expected rate of attrition = 10%

Given the above assumptions, at least 912 randomized subjects (608 Lotus Valve, 304 CoreValve) are needed to account for attrition.

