#### **12.1.4. Baseline Comparability**

Baseline data will be summarized by treatment group for the randomized subjects and separately for subjects in the roll-in (with the 23 mm, 25 mm, or 27 mm Lotus Valve), Lotus 21 mm Nested Registry, LOTUS Edge Nested Registry, roll-in with the 29 mm LOTUS Edge Valve, LOTUS Edge 29 mm Nested Registry, and U.S. Continued Access Study cohorts. Subject demographics, clinical and neurological history, risk factors, and preprocedure characteristics will be summarized using descriptive statistics (e.g., mean, standard deviation,  $n$ , minimum, maximum) for continuous variables and frequency tables or proportions for discrete variables. Treatments for the randomized subjects will be compared with a chi-square or Fisher exact test for discrete variables and a Student  $t$ -test for continuous variables. Treatment differences for the randomized subjects and their 95% confidence intervals will be presented. Procedural characteristics will be summarized similarly. No formal statistical testing will be done for the roll-in (with the 23 mm, 25 mm, or 27 mm Lotus Valve), Lotus

21 mm Nested Registry, LOTUS Edge Nested Registry, roll-in with the 29 mm LOTUS Edge Valve, LOTUS Edge 29 mm Nested Registry, or U.S. Continued Access Study subjects.

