#### **12.1.5. Post-procedure Measurements**

Post-procedure information will be collected at regularly scheduled follow-up examinations as detailed in the clinical study schedule (Table 11.1-1) and will be summarized using descriptive statistics for continuous variables (e.g., mean, standard deviation, n, minimum, maximum) and frequency tables or proportions for discrete variables. Estimates will be reported by treatment group and, for randomized subjects, differences between treatment groups and their 95% confidence intervals will be presented. Treatments for the randomized subjects will be compared with the chi-square or Fisher exact test for discrete variables and the Student t-test for continuous variables. No inferences are planned on the additional measurements and, therefore, alpha-adjustments for multiple comparisons will not be used. The Kaplan-Meier product-limit method will be used to estimate rates for time-to-event endpoints and treatment groups will be compared using the Log-rank and Wilcoxon tests. Adverse event and SAE rates will be reported. No formal statistical testing will be done for the roll-in (with the 23 mm, 25 mm, or 27 mm Lotus Valve), Lotus 21 mm Nested Registry, LOTUS Edge Nested Registry, roll-in with the 29 mm LOTUS Edge Valve, LOTUS Edge 29 mm Nested Registry, or U.S. Continued Access Study subjects.

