### **12.2.3. Randomization Scheme**

A computer generated list of random treatment allocations (i.e., a randomization schedule) will be used to assign subjects to treatment in a 2:1 ratio of Lotus Valve to CoreValve. Randomization will be stratified by center and risk factor (extreme and high operative risk with a targeted enrollment of at least 30% of subjects in each group; see Table 26.2-1 for operative risk definitions). Additional information is provided in the study Manual of Operations.

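### Naming the Student t-test for post-randomization continuous measures under 2:1 allocation risks miscalibrated p-values and intervals; Welch with a matching interval is a near-free improvement

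*Combined protocol and SAP*

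**What the plan says.** For post-procedure measurements in the randomized arms, section 12.1.5 uses a chi-square or Fisher exact test where the variable is discrete, and "the Student t-test for continuous variables". For randomized subjects it adds that "differences between treatment groups and their 95% confidence intervals will be presented". It then qualifies their status: "No inferences are planned on the additional measurements and, therefore, alpha-adjustments for multiple comparisons will not be used".

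Section 12.1.4 names the same test for baseline data, states that "Treatment differences for the randomized subjects and their 95% confidence intervals will be presented", and says procedural characteristics are handled in a similar way.

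On allocation, section 12.2.3 says that a computer-generated list "will be used to assign subjects to treatment in a 2:1 ratio of Lotus Valve to CoreValve". Section 12.1.2.2.1 gives the arm sizes: "at least 912 randomized subjects (608 Lotus Valve, 304 CoreValve) are needed to account for attrition".

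Neither 12.1.4 nor 12.1.5 says whether variances are pooled, names an unequal-variance alternative, or says how the intervals are constructed.

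**The concern.** The ordinary Student t-test uses one pooled variance. With equal arms that does little harm in large samples. With 2:1 allocation, the pooled variance is weighted toward the larger Lotus arm, while the smaller CoreValve arm contributes more to the true standard error of the difference. If CoreValve is the more variable arm, the pooled standard error is too small; if Lotus is, it is too large.

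The measures exposed to this are those that can depend on the device: gradients, orifice area, peak velocity, gait speed and questionnaire scores (section 7.2), and procedure and catheter times (sections 11.7.1 and 11.7.2.2). One valve is mechanically expanded and locked, the other self-expanding, so equal spread is not guaranteed by design. At stake is whether a reported 95% interval for a mean difference covers at 95%.

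**Working it through.** **The plan's own figures.** The plan gives no sample size, power or SD for a between-arm continuous comparison, so there is no stated figure to reproduce for this test. The stated binary calculations do reproduce without any t-test:
- Effectiveness non-inferiority: Farrington-Manning power is 0.801 at 546 vs 273, and 819 is the smallest total reaching 80%. 819/0.90 = 910, against 912 planned.
- Safety: power 0.854 (stated about 85%).
- Effectiveness superiority: N = 684 as stated; power 0.866 at the planned enrolment (stated about 86%).
- Secondary endpoint: power 0.864 (stated about 86%).

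**Inputs.**
- Arms of 608 and 304 (section 12.1.2.2.1).
- With the 25% attrition assumed for the 1-year echo endpoint (section 12.1.3.2): 608 × 0.75 = 456 and 304 × 0.75 = 228.
- k = CoreValve SD / Lotus SD. This is an assumption, shown as a range, because the documents give no CoreValve SD.

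**Formula.** Set the Lotus SD to 1, with n CoreValve and 2n Lotus subjects. For large n:
- Pooled variance of the difference: [(2 + k²)/3] × [3/(2n)] = (2 + k²)/(2n).
- True variance of the difference: 1/(2n) + k²/n = (1 + 2k²)/(2n).
- Ratio of pooled to true standard error: R = √[(2 + k²)/(1 + 2k²)].
- True two-sided type I error at nominal 5%: 2 × [1 − Φ(1.96 R)].
- A pooled 95% interval has R times the correct width.

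Example, k = 1.5: R = √(4.25/5.5) = 0.879; 1.96 × 0.879 = 1.72; type I error about 8.5%, so coverage about 91.5%.

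| k | R | Type I error | Pooled 95% interval |
|---|---|---|---|
| 0.67 | 1.138 | 2.6% | 14% too wide |
| 0.80 | 1.076 | 3.5% | 8% too wide |
| 0.90 | 1.036 | 4.2% | 4% too wide |
| 1.00 | 1.000 | 5.0% | correct |
| 1.10 | 0.969 | 5.8% | 3% too narrow |
| 1.25 | 0.929 | 6.9% | 7% too narrow |
| 1.50 | 0.879 | 8.5% | 12% too narrow |

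**Simulation check.** With 400,000 simulated normal trials per setting, at both 608/304 and 456/228, the pooled test agreed with the table to within about 0.1 percentage point. Welch's test stayed at 4.9% to 5.0% at every ratio from 0.5 to 2.0.

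**Role of allocation.** With 1:1 arms the two variances above become equal for any k. Simulation at k = 1.5 with equal arms gave 5.0% for the pooled test. The unequal allocation is what creates the exposure.

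**Scale, as illustration only.** Table 4.1-4 gives Lotus mean-gradient SDs of 6.77 mmHg at 30 days and 5.35 at 1 year, a ratio of 1.27. If a gap of that size lay between the arms, type I error would be about 7.0% or 3.4%, depending on direction. Both SDs are from Lotus, so they say nothing about CoreValve.

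**The case against.** The strongest reply has four parts.

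1. *The pooled form is never written.* True. A reader might infer that the plan has chosen a pooled-variance test and pooled intervals. The text supports only a test name that conventionally means equal variance, and intervals of unstated construction that are not tied to the t-test. Section 12.2 also refers analyses to a study-specific SAP, which could settle the form; the combined document as released contains no such text. This limits the point to how the wording is ordinarily read. It does not remove it, because leaving the form open is also worth correcting.

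2. *The measures are declared non-inferential.* True, and it caps the importance. The sentence explains why no alpha adjustment is made; it does not stop tests and 95% intervals from being reported, and a descriptive 95% interval should still cover at 95%.

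3. *Baseline variables are not at risk.* This stands in full. Randomization gives them the same distribution, hence the same variance, in both arms. A reader might extend the concern to all of 12.1.4; only procedural characteristics, which arise after randomization and can depend on the device, belong in it.

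4. *There is no evidence of unequal SDs.* This also stands. It is tempting to say every reported mean difference will carry wrong error bars. The documents do not support that: the error is small when SDs are close, and nothing in them shows how close they are. Different expansion mechanisms make unequal spread possible but do not establish it.

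**Conclusion.** The point holds as a minor improvement in specification. Under the conventional reading of the test name, with 2:1 allocation, p-values and any intervals built on the pooled standard error may be off in either direction for post-randomization continuous measures. The size rests wholly on an assumed SD ratio and approximately normal means: material at ratios around 1.25 to 1.5 or their inverses, negligible within 10% of equality.

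A reader might infer a threat to the trial's main claims. There is none: the safety, effectiveness and secondary endpoints are all binary and use Farrington-Manning or chi-square tests (sections 12.1.1 to 12.1.3), so no success criterion, sample size or power depends on a t-test. What makes the change worthwhile is that the alternative is valid whether or not the SDs are equal.

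**What to change.** In section 12.1.5, and for procedural characteristics in 12.1.4, replace the Student t-test with the Welch (Satterthwaite) unequal-variance t-test. State that the 95% confidence interval for a mean difference uses the same standard error and degrees of freedom. The test for true baseline variables can stay as it is. Carry the same wording into the SAP; section 12.3.5 provides the route, an amended SAP approved before the analyses are run.

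The cost is a change of wording. Welch's test is standard software output, and at these arm sizes the loss of power when variances are equal is negligible.

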REPRISE III: REpositionable Percutaneous Replacement of Stenotic Aortic Valve through Implantation of Lotus™ Valve System – Randomized Clinical Evaluation	
	the LOTUS Edge Valve, up to 20 subjects will be enrolled in the LOTUS Edge 29 mm Valve roll-in phase (29 mm valve only; a minimum of 2 roll-in subjects per center) before enrolling in the LOTUS Edge 29 mm Nested Registry.
Primary Endpoints	
Primary Safety Endpoint: Composite of all-cause mortality, stroke, life-threatening and major bleeding events, stage 2 or 3 acute kidney injury, or major vascular complications at 30 days
 
Primary Effectiveness Endpoint: Composite of all-cause mortality, disabling stroke, or moderate or greater paravalvular aortic regurgitation (based on core lab assessment) at 1 year
 
Powered statistical analyses for the primary safety endpoint and the primary effectiveness endpoint will be carried out on the randomized cohort.

Secondary Endpoint	
Moderate or greater paravalvular aortic regurgitation (based on core lab assessment) at 1 year
 
Powered statistical analysis for the secondary endpoint will be carried out on the randomized cohort.

Additional Measurements	
Additional measurements based on the VARCa,b endpoints and definitions (see Note 1 below) will be collected peri- and post-procedure, at discharge or 7 days post-procedure (whichever comes first), 30 days, 6 months, and 1, 2, 3, 4, and 5 years post index procedure, unless otherwise specified below.
 
 
• Safety endpoints adjudicated by an independent Clinical Events Committee (CEC): 
 
○ Mortality: all-cause, cardiovascular, and non-cardiovascular
 
○ Stroke: disabling and non-disabling
 
○ Myocardial infarction (MI): periprocedural (≤72 hours post index procedure) and spontaneous (>72 hours post index procedure)
 
○ Bleeding: life-threatening (or disabling) and major
 
○ Acute kidney injury (≤7 days post index procedure): based on the AKIN System Stage 3 (including renal replacement therapy) or Stage 2
 
○ Major vascular complication
 
○ Repeat procedure for valve-related dysfunction (surgical or interventional therapy)
 
○ Hospitalization for valve-related symptoms or worsening congestive
 
 
 

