REPRISE III: REpositionable Percutaneous Replacement of Stenotic Aortic Valve through Implantation of Lotus™ Valve System – Randomized Clinical Evaluation	
	
study performed will be used for analysis.
 
Note 4: For subjects diagnosed with a neurological event (e.g., stroke, transient ischemic attack), a neurological physical exam (conducted by a neurologist, neurology fellow, neurology physician assistant, or neurology nurse practitioner), NIHSS assessment, and mRS must be performed after the event; mRS must also be administered 90±14 days post-neurological event.
 
a: Kappetein AP, et al. J Am Coll Cardiol. 2012;60:1438
 
b: Leon M, et al. J Am Coll Cardiol. 2011;57:253

Follow-up Schedule	All subjects implanted with a test or control device will be assessed at baseline, peri- and post-procedure, at discharge or 7 days post-procedure (whichever comes first), 30 days, 6 months, 1 year, and then annually for up to 5 years post-procedure. Subjects who are enrolled but not implanted with a test or control device at the time of the procedure will be followed for safety through 1 year.
Study Duration	Subjects implanted with a test or control device will be followed for 5 years after the procedure.

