**Table 4.1-3: 1-Year and 2-Year Outcomes in REPRISE II Main Cohort (N=120)**

Outcomes	REPRISE II 1 Year	REPRISE II 2 Years
----------	----------------------	-----------------------

Clinical event rates are presented as Kaplan-Meier estimates.

References: Meredith, 2015, 2016

The REPRISE II study was subsequently expanded to enroll 130 additional subjects in the REPRISE II extended trial cohort at centers in Australia and Europe; enrollment in this extended cohort was completed in April 2014. The main trial cohort and the extended trial cohort had the same overall study design. The main trial cohort received additional neurologic evaluation and annual imaging assessments to determine valve frame integrity. Per the protocol, a statistically powered analysis based on the combined main and extended trial cohorts (full cohort, N=250) was performed for the primary safety endpoint (mortality at 30 days). The primary safety endpoint was analyzed on an intent-to-treat basis (all subjects enrolled, whether or not a study device is implanted). A one-sample z test was used to test the one-sided hypothesis that 30-day all-cause mortality is less than the prespecified PG of 16% (based on an expected rate of 9.8% plus a testing margin of 6.2%). All-cause mortality at 30 days was 4.4% with an upper confidence bound of 6.97% and the primary safety endpoint was met.

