#### 12.1.1.3. Statistical Methods – Primary Safety Endpoint

All subjects who are enrolled and randomized will be eligible for evaluation. Any events or hospitalizations occurring after enrollment but prior to the index procedure should be entered in the electronic data capture system; events with onset date starting from the time of the index procedure will be included in the primary endpoint analysis.

Handling of dropouts and missing data will depend on their frequency and the nature of the outcome measure. Sensitivity analyses (e.g., tipping-point analysis) will be performed to assess the impact of subjects with inadequate follow-up (i.e., missing data) on the primary endpoint and to assess the robustness of the conclusion of the primary analysis. The sensitivity analysis of the primary endpoint, including events occurring after enrollment but prior to the index procedure, will be performed. Statistical models that account for censored data will be employed in appropriate circumstances (e.g., for time-to-event outcomes). Suspected invalid data will be queried and corrected in the database prior to statistical analysis. Additional information may be found in the Statistical Analysis Plan.

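### Section 12.1.5 gives Kaplan-Meier rates for non-fatal time-to-event endpoints with no competing-risk handling of death, which overstates late-event risk (endocarditis, thrombosis) at 3 to 5 years and matters little for early events

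*Combined protocol and SAP*

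**What the plan says.** Section 12.1.5 (Post-procedure Measurements) states that "The Kaplan-Meier product-limit method will be used to estimate rates for time-to-event endpoints" and that "treatment groups will be compared using the Log-rank and Wilcoxon tests". It does not list which endpoints count as time-to-event. The same section allows "frequency tables or proportions for discrete variables" and says "No inferences are planned on the additional measurements".

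The Synopsis schedules the additional measurements at "30 days, 6 months, and 1, 2, 3, 4, and 5 years post index procedure", unless otherwise specified, and adds that "Subjects implanted with a test or control device will be followed for 5 years after the procedure". Section 12.2.4 sets event cut-offs for each year up to year 5. The events adjudicated by the Clinical Events Committee (CEC, Section 7.2) include stroke, new pacemaker, repeat procedure, hospitalization, valve thrombosis and endocarditis, all of which can be non-fatal.

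The only other text on censoring is in Section 12.1.1.3: "Statistical models that account for censored data will be employed in appropriate circumstances". The supplied text nowhere mentions competing risks, cumulative incidence, or what happens to a subject who dies without the event. The sponsor's earlier REPRISE II table (Table 4.1-3) lists stroke, pacemaker and endocarditis under the footnote "Clinical event rates are presented as Kaplan-Meier estimates".

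**The concern.** The randomized population is at high or extreme operative risk, so many subjects will die during 5 years of follow-up. If a death without the event is censored, Kaplan-Meier estimates the risk in a hypothetical population in which nobody dies. The proportion of treated patients who will actually have the event is lower, because the dead can no longer have it.

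The two figures agree until event-free deaths precede later events, and they separate from then on. The endpoints most exposed are therefore those that keep occurring in years 2 to 5. These rates will be read as the valve's absolute long-term risks, so the estimator decides what the reader is told.

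**Working it through.** **1. The mechanism in the documents' own table.** Table 4.1-3 (REPRISE II main cohort, N=120) gives 2-year endocarditis as 2.8% with 3 events, 1 of them in the first year, and 2-year mortality as 16.9% with 20 deaths. Event times are not given, so the risk sets are approximate: about 113 for the first event and about 103 for the two in year 2 (120 × 0.89 = 107 falling to 120 × 0.831 = 100).

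- Deaths removed from the risk set: 1 − (1 − 1/113)(1 − 1/103)² = 2.80%, which matches 2.8%.
- Deaths kept in the denominator: 3/120 = 2.5%.
- Mortality itself is 16.9% by Kaplan-Meier and 20/120 = 16.7% crude, so other censoring is slight and the gap is mainly due to deaths.

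**2. Size at 2 years.** To allow for that slight other censoring, the crude count is divided by an effective N of 20/0.169 = 118.3.

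| 2-year endpoint | Events | Kaplan-Meier | Events/118.3 | Relative excess |
|---|---|---|---|---|
| Endocarditis | 3 | 2.8% | 2.5% | +10% |
| Valve/CHF hospitalization | 9 | 8.0% | 7.6% | +5% |
| Stroke | 11 | 9.5% | 9.3% | +2% |
| Pacemaker | 40 | 34.2% | 33.8% | +1% |

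The published rates are rounded to one decimal, so excesses of 1% or 2% are at the limit of what this comparison can show.

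**3. Mortality assumed to 5 years.** The documents give no 5-year mortality. From Tables 4.1-2 and 4.1-3, mortality is 4.2% at 30 days, 11.0% at 1 year and 16.9% at 2 years. The second-year hazard is ln(0.89/0.831) = 0.0686 per year. If it continues, survival at 5 years is 0.831 × exp(−3 × 0.0686) = 0.676, so about 32% have died.

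**4. Event models.** Let *a* be the fraction with the event by 30 days, *h* the later hazard, and S(u) survival from death, with the hazards independent.

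- Kaplan-Meier: 1 − (1 − a)exp(−ht)
- Cumulative incidence: a + ∫₀ᵗ h(1 − a)exp(−hu)S(u)du

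Inputs:

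- Endocarditis: a = 0, h = −ln(1 − 0.028)/2 = 0.0142.
- Thrombosis: a = 0, h = −ln(1 − 0.012) = 0.0121, from 3/249 at 1 year in Table 4.1-4 and assumed constant.
- Pacemaker: a = 0.291, h = ln(0.709/0.658)/2 = 0.0373, from 29.1% at 30 days and 34.2% at 2 years.
- Stroke: a = 0.061 from Table 4.1-2, h = 0.01 assumed. This does not reproduce the 9.5% seen at 1 and 2 years, so the stroke row is illustrative only.

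**5. Results at 5 years.** The third column uses the 32% mortality of step 3. The last column uses a constant death hazard giving 30% and 60% mortality.

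| Endpoint | Kaplan-Meier | Cumulative incidence (32% dead) | Excess (32% dead) | Relative excess, 30% to 60% dead |
|---|---|---|---|---|
| Endocarditis | 6.85% | 5.55% | 1.3 points, +23% | +19% to +52% |
| Thrombosis | 5.86% | 4.74% | 1.1 points, +23% | +19% to +52% |
| Stroke | 10.68% | 9.81% | 0.9 points, +9% | +7% to +17% |
| Pacemaker | 41.17% | 38.91% | 2.3 points, +6% | +5% to +11% |

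Repeat procedure for valve dysfunction had no events in REPRISE II through 2 years in the main cohort (1 year in the full cohort), so on that evidence both estimators give zero.

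**The case against.** The strongest reply has four parts.

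- **The text is incomplete.** Section 12.1.5 does not say that death is censored and does not name the endpoints. It allows simple proportions for discrete variables, and the 1-year REPRISE II full-cohort rates (Table 4.1-4) are plain proportions with deaths in the denominator. The protocol also defers detail to a Statistical Analysis Plan that is not reproduced in the supplied text and could handle death properly. This stands as a limit on certainty. It does not remove the point: the Kaplan-Meier sentence is the specific rule for time-to-event endpoints, and Table 4.1-3 shows the sponsor applying it to these very events.
- **Several endpoints are early.** In REPRISE II, stroke stood at 11 events at both 1 and 2 years, and 34 of the 40 two-year pacemakers were in place by 30 days. Coronary obstruction, septal perforation, mitral damage and tamponade are limited to 72 hours, and acute kidney injury to 7 days. This stands, and it is why the effect is uneven.
- **Nothing is tested on these rates.** This also stands. Both primary composites include death and are compared as rates, and the secondary endpoint uses a chi-square test. The log-rank test remains valid for cause-specific hazards. Descriptive status does not, however, correct an absolute risk that is too high.
- **Larger figures overreach.** With a constant 3% per year event hazard (assumed), 5-year Kaplan-Meier is 13.9%. Holding the 11.6% first-year mortality of Table 4.1-4 constant gives a cumulative incidence of 10.5% (ratio 1.33). A 25% yearly mortality inferred from the planned 32% composite gives 7.5% (ratio 1.85). These imply about 46% and 76% dead at 5 years. The documents show a lower second-year hazard and state no mortality component for the composite, so they do not support either ratio as the expected size.

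**Conclusion.** The point holds in a limited form. As written, the plan yields reported risks that are never below the cumulative incidence, and above it for non-fatal events that continue to occur after deaths have accrued. The practical consequence is confined to late events at 3 to 5 years, chiefly endocarditis and thrombosis. For stroke and pacemaker it is small, and for periprocedural events negligible.

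The direction follows from the estimator once deaths are censored. The sizes rest on assumed 5-year mortality, assumed constant late hazards and independence of the two hazards.

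A reader might also infer that the bias will differ between the Lotus and CoreValve arms and so distort their comparison. That would follow only if mortality differs between arms, and the plan states no arm-specific mortality, so it remains a possibility. Nor do the documents support reading this as a flaw in the primary or secondary analyses.

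**What to change.** In Section 12.1.5, and in the Statistical Analysis Plan:

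- Use Kaplan-Meier only for all-cause death and for composites that include it.
- For every other time-to-event endpoint, report the Aalen-Johansen cumulative incidence with death as the competing event. For cardiovascular death, non-cardiovascular death is the competing event.
- Keep the log-rank test, labelled as a comparison of cause-specific hazards.
- Footnote the Kaplan-Meier figure where comparability with earlier studies is wanted.
- List the endpoints that are treated as time-to-event.

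The cost is a short text change and a programming option, with no new data and no effect on sample size. The downside is that reported rates will be slightly lower than Kaplan-Meier-based historical figures, which the footnote addresses.
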